	Innovation program.
Key Protocol Contributors	[name] MB BCh BAO, MBA, DPM, MEPM
	PGCert
	Clinical Lead Digital ECMT
	The University of Manchester, CRUK Manchester
	Institute, Oglesby Cancer Research Centre, [name]
	[name]
	[contact]
	[name]
	Consultant Medical Oncologist
	The Christie NHS Foundation Trust, [name],
	[name]
	[contact]

[name]
Clinical Trial Coordinator
The University of Manchester, CRUK Manchester
Institute, Oglesby Cancer Research Centre, [name]
[name]
[contact]
[name]
Project Manager
The University of Manchester, CRUK Manchester
Institute, Oglesby Cancer Research Centre, [name]
[name]
[name], MD, PhD, Medical oncologist
[name]
[name], the Netherlands
E-mail: [contact]
[name]
Research Practitioner
The Christie NHS Foundation Trust, [name],
[name]
[contact]

STUDY SUMMARY

Study Title	User experience study of digital tools to collect data on			
	wellbeing and side effects in cancer patients.			
Study Design	Feasibility study			
Study Participants	 All patients enrolled in phase 1 or 2 anticancer drug trials and; Healthcare professionals (medical oncologists, nurse practitioners) monitoring these patients. 			
Planned Size of Sample	Patients included in investigation	Patients included in investigational drug trials, expected		
	number around 60. Also, a mir	nimum of 1 Healthcare		
	professional at each site in the	study.		
Planned Study Period	4 weeks			
	Objectives	Outcome Measures		
Primary	To evaluate the feasibility of using digital tools to report effects of drugs in patients on phase 1 or 2 anticancer drug trials	 Number of patients screen failing or withdrawing from study Proportion of patients complying with agreed scheduled use of the tool (daily for 28 days). 		
Secondary	To evaluate user experience of using different digital tools to self-report on adverse events and quality of life.	 End of study questionnaire completed by patients. Semi-structured interviews with healthcare professionals. 		

Exploratory	Explore the richness of the data reported by patients using digital tools and validated quality of life instrument.	 Output of PROACT 2.0 questionnaire and analysed videos. Output of validated quality of life instrument – EQ5D5L
Selection criteria		
Inclusion Criteria	 Patients in screening for participation in a phase 1-2 anticancer drug trial Written informed consent to participate in the study. 	
Exclusion Criteria	 Not capable of using mobile phone applications, or no carer who is willing to and able to use the applications on the participants behalf. Enrolled in a phase 1-2 anticancer drug trial that includes a QoL questionnaire, where inclusion of an additional QoL would interfere with the study's intended QoL measurements. This is at the investigator's discretion. 	

FUNDING AND SUPPORT IN KIND

FUNDER(S)

Horizon 2020 European Union Funding for Research & Innovation program.

Grant agreement number: 965397

KEY WORDS: Digital tools; PROACT 2.0; toxicity; phase 1; phase 2.

ABBREVIATIONS	
AE	Adverse Event
CCE-DART	Cancer Core Europe – DATa Rich clinical Trials
CTIMP	Clinical trial of investigational medicinal product
DLT	Dose Limiting Toxicity
GCP	Good Clinical Practice
HRQoL	Health-related Quality of Life
IMP	Investigational medicinal product
NKI	Netherlands Cancer Institute
PIS	Patient Information Sheet
PROACT 2.0	Patient Reported Outcomes about Clinical Tolerability version 2.0
QoL	Quality of Life
PRO-CTCAE	Patient-Reported Outcome - Common Terminology Criteria for Adverse Events
GCP	Good Clinical Practise
GCP GDPR	Good Clinical Practise General Data Protection Regulation
GCP GDPR eCRF	Good Clinical Practise General Data Protection Regulation Electronic Case Report File
GCP GDPR eCRF CRF	Good Clinical Practise General Data Protection Regulation Electronic Case Report File Case Report File

STUDY PROTOCOL

1 BACKGROUND

1.1 Overview

Precision cancer medicine has created a rapid evolution of clinical research, with new types of adaptive, basket and umbrella clinical trials, amongst others, currently being developed with the aim of optimizing the biomarker-drug co-development process tailored to each disease setting¹. However, all too often, cancer patients receive treatments which can be toxic, ineffective, or both². Since cancer treatments often have a narrow therapeutic index, it is more important than ever to conduct smarter clinical trials which more effectively identify toxicities that significantly impact a patient's quality of life so we can truly deliver the right drug, for the right patient, at the right time, with the right tolerability profile.

1.2 Adaptive clinical trial designs

Clinical trials are the best source of clinical evidence but in many prospective trials, novel treatments are tested in large, unselected patient populations, the average effect size is modest, and the reasons for response / non-response in individual patients are poorly understood². Platform trials enable the acquisition of prospective data from multiple patient cohorts and facilitate the study of biomarkers associated with chemosensitivity. However, current studies still are too rigid and have too many limitations that do not allow them to adapt to the speed of the discoveries in the oncology field, especially in the academic setting. In the digital age, new technologies can be adapted to clinical trials to enhance their performance in different ways³.

With the aim of improving the design and implementation of clinical trials, and the use of newer, more effective methods, the CCE-DART project (Cancer Core Europe – Data Rich clinical Trials) was established to address a number of critical issues. Divided into four broad areas these are;

- (i) use of more efficient clinical trial methodology.
- (ii) incorporation of more accurate, integrated, and dynamic imaging and molecular markers of tumour drug response to treatment into the design and implementation of clinical trials.
- (iii) development of digital tools facilitating the trial management and clinical-decisionmaking; and
- (iv) patient empowerment/ engagement.

1.3 Health Related Quality of Life reporting

Side effects, or adverse events (AEs), arising from anticancer therapies can result in a diminished health-related quality of life (HRQoL). Inadequate symptom monitoring and reporting can lead to worsening of AEs, emergency department visits, hospital admissions and increased impact on HRQoL⁴. Studies have demonstrated the importance and value of direct patient involvement in developing an improved understanding of how cancer medicines impact drug tolerability and a patient's quality of life^{5–} ⁷.

The ubiquity and high availability of low-cost smart devices and affordable broadband (4G) is now enabling the development and implementation of new clinical applications, which can enable improved drug side effect monitoring outside of the hospital⁸⁻⁹. Importantly, while the risk of inequality in the context of the digital divide still exists, it is significantly less in the mobile setting, with most of the public having access to technology¹⁰. The OFCOM 2020 report found that 82% of the public have a smartphone, and 87% of the population access the internet. 70% of adults 65-74 access the internet and 49% of 75+ adults¹⁰. Serial capture of these clinical data directly from patients has the potential to transform the patient's role in the clinical trial and provide important and vital information, which can guide optimal dosing and scheduling of cancer therapies.

Over the past 10 years, studies have shown that patient involvement in the reporting of their symptoms has demonstrated differences between what patients identify as important to their quality of life (QoL) compared with physicians^{11–14}. Traditionally, the patient's QoL is assessed at different timepoints in a clinical study using a formally validated HRQoL instrument in the form of a questionnaire. The benefits of assessing patients HRQoL have been well described in the literature^{15,16}. One study compared patient reporting of eight symptoms using the European Organization for the Research and Treatment of Cancer Quality of Life Questionnaire C30 (QLQ-C30 or QLQ), alongside physicians' reporting on the same eight symptoms in the study's adverse events log. This study showed that clinicians significantly under reported patient symptoms in a chemotherapy clinical trial¹⁷. Additionally, a phase 1 study evaluating dose limiting toxicities (DLTs) found that patient-reported assessment of tolerability and toxicity may help to better adapt the standard DLT definition to best define the recommended phase 2 dose¹⁸. Patient engagement and involvement in reporting symptoms is important and enriches the clinical understanding and impact of new and existing cancer therapies.

1.4 Digital solutions

Traditionally, digital solutions have focused on an online or mobile questionnaire-based tool to enable patients to provide information regarding their symptoms while on cancer treatment. These tools have demonstrated clinical utility^{4,19}. The PRO-TECT study evaluated the implementation of electronic patient-reported outcomes (ePROs) utilising the Patient-Reported Outcomes version of the Common Terminology Criteria for Adverse Events (PRO-CTCAE) and their value in the management of patients. This study demonstrated how ePROs improved discussions with patients, empowered patients and improved physician decision making²⁰. Additionally, the clinical utility of an artificial tool was demonstrated in a study showing a 69% reduction in risk of having a pain-related admission during the study for those who used the app²¹.

Furthermore, the original PROACT study (PROACT 1.0 - Patient Reported Outcomes about Clinical Tolerability) demonstrated a new way for patients to interact with technology while on a clinical trial. The PROACT app enabled the capture of additional information by facilitating communication between patients, their clinical team, and feedback to the Sponsor, on specific topics such as safety, dosage administration and study design, while also providing added and complementary information on tolerability¹⁹. PRO-CTCAE is a patient-oriented digital tool to collect AEs from patients in real time. The National Cancer Institute developed the PRO-CTCAE to best capture 78 discrete toxicities in oncology clinical trials through direct patient reporting^{4,22}. Subsequent evaluations of the PRO-CTCAE showed that patients grade symptoms up to 40% higher compared to clinicians²³. The National Cancer Institute adapted these PRO-CTCAE into a diary questionnaire, which can be used on a daily basis for registration of toxicities.

For this study both the PROACT application and PRO-CTCAE questionnaire will be incorporated into the new PROACT 2.0 system to assess the multi-functionality of the system in assessing toxicities.

1.5 Study applications

Part of the CCE-DART project relies on the development and implementation of informatics tools that, alone, will involve important management improvements as they address unmet needs in current clinical trial designs. Some of these tools have already been developed and, under the CCE-DART umbrella, they will be validated, optimised, and refined for their use in a clinical setting. Specifically, the following tool has already been tested in other settings providing the adequate grounds for the estimation of their potential impact:

PROACT 2.0 is a digital healthcare platform which enables patients to self-report how they are feeling and functioning on a clinical trial via text, voice note, video or digital questionnaire. It can also be used to transmit information related to the trial to patients and caregivers through its broadcast functionality. Overall, the PROACT application has been trialled by 30 patients across two 'technology' clinical trials. PROACT 1.0 was trialled in an initial Proof-of-Concept study recruiting 8 patients in 2016 and then 22 patients were enrolled in the PROACT 1.0 study at The Christie NHS Foundation Trust and The Clatterbridge Cancer Centre. The first study reported 41 AEs. In the second study, 131 messages (14 video, 2 audios, 115 text) were sent by patients, 37 message events were associated with 43 AEs and in 32 message events the patients stated that they were in good health. The feedback from patients and nursing staff has been very supportive and positive. PROACT 2.0 has been developed by Fondazione IRCCS Instituto Nazionale dei Tumori di Milano, Italy as part of the Cancer Research UK UpSMART Accelerator Award, taking into consideration feedback from healthcare professionals and patients. Under this protocol the new PROACT 2.0 system will be implemented in a large heterogeneous clinical setting for the first time¹⁹, focusing on two of the features of this digital tool – video and the digital questionnaire.

The PRO-CTCAE digital questionnaire will be uploaded into PROACT 2.0 for this study, and it will be the first time that this digital questionnaire will be implemented in a large clinical patient cohort.

1.6 Study Proposal

This is a feasibility, non-CTIMP study within CCE-DART, designed to investigate the feasibility of collecting QoL information from patients via digital tools. By feasibility, we mean the assessment of the uptake of the tool, the compliance to schedule and the quality of the data collected. Additionally, we aim to better understand the experience of patients and healthcare professionals in the use of digital tools to collect clinical data on well-being and adverse events. The study will be conducted alongside the patient's standard care and will not interfere in their trial-specific treatment.

This study will form part of a package of work within the CCE-DART project. This work package (WP12) aims to study and implement digital tools in clinical trials within Cancer Core Europe. It is important to note that this is not a Medical device Reporting (MDR) study.

1.7 Patient and Public Involvement

Over several years there has been continuous and extensive input from patients throughout the development of the PROACT tool and the development of this and previous protocols. The PROACT 1.0 application was originally designed with full patient involvement, and feedback on the utility of the

PROACT 1.0 tool was provided by patients and healthcare professionals at the end of the original study. Furthermore, the PROACT 2.0 system has been trialled in a feasibility study of 20 patients with positive feedback.

Additionally, patients were consulted on the usefulness of collecting HRQoL data and how they felt it would benefit them and their care. Feedback from interviews with patients indicated that they were enthusiastic about the prospect of monitoring HRQoL parameters that impacted areas of their life that were important to them, e.g., going for a walk every day. They wanted to have the opportunity to set these goals prior to the start of their treatment. Further patient engagement was carried out to assess the use of technology in the collection of HRQoL assessments. Understandably there were concerns about the potential to exclude technology illiterate patients from studies; however, they did concede that due to the COVID-19 pandemic older patients have become more technologically savvy. They stressed, in strong terms, their support for the study and its aims. The majority favoured the use of a video as a training method to show how to use the technology in the study.

Objective	Measures
Primary Objective To evaluate the feasibility of using digital tools to report effects of drugs in patients on phase 1 or 2 anticancer drug trials	 Number of patients screen failing or withdrawing from study. Proportion of patients complying with agreed scheduled use of the tool (daily for 28 days).
Secondary Objective To evaluate user experience of using different digital tools to self-report on adverse events and quality of life.	 End of study questionnaire completed by patients. Semi-structured interviews with healthcare professionals.
Exploratory Objective Explore the richness of the data reported by patients using digital tools and validated quality of life instrument.	 Output of PROACT 2.0 questionnaire and analysed videos. Output of validated quality of life instrument – EQ5D5L.

2 OBJECTIVES AND OUTCOME MEASURES/ ENDPOINTS

3 RESEARCH QUESTIONS

The aim of this study is to evaluate the feasibility of using digital applications to report the effects of investigational medicinal products (IMP) on the quality of life of cancer patients.

The research hypothesis is that using patient centered tools, such as PROACT 2.0, improves our understanding of QoL through proactive and dynamic engagement with patients. We hypothesise that this engagement will: help reduce recall bias; ensure we are capturing QoL data important to patients; and, more importantly, will allow healthcare teams to proactively engage with patients and intervene earlier where issues are reported. Furthermore, real time reporting of IMP toxicities will allow for a more comprehensive understanding of IMP profiles.

3.1 Objectives

3.1.1 Primary Objective

To evaluate the feasibility of using digital tools to report effects of drugs in patients on phase 1 or 2 anticancer drug trials.

3.1.2. Secondary objectives

To evaluate user experience of using the different digital tools to self-report on adverse events and quality of life.

3.1.3 Exploratory objectives

Explore the richness of the data reported by patients using digital tools and validated quality of life instrument.

3.2 Outcomes

3.2.1 Primary outcomes

The primary outcome measures for this study are:

- Number of patients screen failing or withdrawing from study
- Proportion of patients complying with agreed scheduled use of the digital tools (daily for 28 days).

Adherence to agreed usage schedule of at least 75% would be considered acceptable for feasibility for assessment of the digital tools.

3.2.2 Secondary outcomes

The secondary outcomes are

- End of study questionnaire complete by patients.
- Semi-structured interviews with healthcare professionals.

3.2.3 Exploratory objectives

The exploratory outcomes of this study are:

- Output of PROACT 2.0 questionnaire and analysed videos.
- Output of validated quality of life instrument EQ5D5L

4 STUDY DESIGN

4.1 Overview

This is a feasibility study evaluating whether patients receiving anticancer treatment in phase 1 or 2 anticancer drug trials executed in Cancer Core Europe Centres will use digital applications to record HRQoL data. It will also assess the user experiences of patients and healthcare professionals of PROACT 2.0. The study will be performed in accordance with Good Clinical Practise (GCP), and all key trial personnel will be appropriately trained.

4.2 Trial Population

All potential study participants will be seen and assessed against eligibility criteria whilst already enrolled (cannot have started treatment) or attending for consideration for participation in a phase 1 or 2 clinical trials. Study participants will be selected by treating physicians from the several Cancer Core Europe centres participating in the DART WP12 project. Potential participants will be provided with a patient information sheet (PIS) and invited to voluntarily consent to participate in the feasibility study. It should be made clear to the potential trial participant that consent is voluntary and can be withdrawn at any time without any impact on their ongoing medical care.

If a potential participant declines entry into the study, the reasoning for this will be documented in the screening log where possible.

Potential study participants should be given sufficient time to consider participation in this study before consent is elicited. No activities for the study can be undertaken before consent had been obtained. After consent has been received the patient will be formally assessed for eligibility for the study against inclusion and exclusion criteria of the study protocol.

5 RECRUITMENT AND TRIAL PROCEDURES

5.1 Inclusion criteria

There will be no exception to the eligibility requirements at the time of registration. Patients are eligible if all inclusion criteria are met and none of the exclusion criteria apply.

- 1. Screening for participation in a phase 1-2 anticancer drug trials.
- 2. Written informed consent to participate in the study.

5.2 Exclusion criteria

A potential participant who meets any of the following criteria will be excluded from participation in this study:

- 1. Not capable of using mobile phone applications, or no carer who is willing to and able to use the applications on the participants behalf.
- 2. Enrolled in a phase 1-2 anticancer drug trial that includes a QoL questionnaire, where inclusion of an additional QoL would interfere with the study's intended QoL measurements. This is at the investigator's discretion.

A patient can be supported in this study by a carer e.g. if the patient does not have access to a suitable device but a carer is willing to provide access to one for them. However, the role of the carer should be limited to support in accessing the tool and they should not complete the videos or questionnaires on the patients behalf.

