5.4 Recruitment

Patients in screening for a phase 1-2 trial will be informed of this feasibility study and given the PIS by their treatment team. Patients must not have commenced treatment in order to qualify to join the feasibility study. For trial entry a patient must fulfil all inclusion criteria and no exclusion criteria; this preliminary check against eligibility will be conducted by the patient's treating clinician.

A patient can be supported in this study by a carer e.g. if the patient does not have access to a suitable device but a carer is willing to provide access to one for them. However the role of the carer should be limited to support in accessing the tool and they should not complete the videos or questionnaires on the patients behalf.

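### Exclusion criterion 1 as written turns away app-capable patients who have no carer, and its carer clause contradicts the rule that carers must not complete entries

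*Protocol*

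**What the plan says.** Protocol Section 5.2 lists as its first exclusion criterion "Not capable of using mobile phone applications, or no carer who is willing to and able to use the applications on the participants behalf". The Study Summary repeats the sentence. Section 5.2 introduces its list with "A potential participant who meets any of the following criteria will be excluded from participation in this study", and Section 5.1 adds: "There will be no exception to the eligibility requirements at the time of registration".

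The paragraph under the list describes the carer differently. It begins "A patient can be supported in this study by a carer e.g. if the patient does not have access to a suitable device", goes on to say that "the role of the carer should be limited to support in accessing the tool", and says of carers that "they should not complete the videos or questionnaires on the patients behalf". Section 5.4 repeats the rule: "However the role of the carer should be limited to support in accessing the tool and they should not complete the videos or questionnaires".

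Section 5.7.2 and Table 1 in Section 6 define app use in the two PROACT 2.0 arms as a daily video or a daily questionnaire for four weeks. Section 3.2.1 names two primary outcomes: the number of patients who fail screening or withdraw, and the proportion who comply with the daily schedule. Adherence of at least 75% is called acceptable.

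**The concern.** The criterion has two separate faults.

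The first is the connective. A carer clause in such a criterion normally exists to let in patients who need help. Joined by *or*, it does the reverse: lack of a carer becomes a reason for exclusion in its own right, even for someone fully able to use the app.

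The second is the carer's role. The criterion looks for a carer who will operate the app in the patient's place. The paragraph beneath it confines the carer to helping with access and forbids the carer to make the entries.

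In a feasibility study, who can take part and who actually makes the entries are part of the question being asked. If sites resolve the sentence differently, they enrol from different populations, and both primary outcomes are affected.

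**Working it through.** No formula applies and the plan gives no figure to reproduce. The check is one of logic and of setting the sections side by side.

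**Step 1: the connective.** Let A be *not capable of using the app* and B be *no willing and able carer*. Section 5.2 excludes on A or B. The alternative, suggested by the optional carer wording, is A and B.

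| Patient | As written (A or B) | If joined by *and* (A and B) |
|---|---|---|
| Capable, has carer | eligible | eligible |
| Capable, no carer | excluded | eligible |
| Not capable, has carer | excluded | eligible |
| Not capable, no carer | excluded | excluded |

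The two rules differ in two of the four rows. As written, only a capable patient with a carer is eligible, and a carer never makes an incapable patient eligible. This conflicts with Sections 5.2 and 5.4, where a patient may have a carer's support but need not.

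**Step 2: the carer's role.** The criterion refers to "no carer who is willing to and able to use the applications on the participants behalf". The rule below it, repeated in Section 5.4, limits the carer to access and bars the carer from completing videos or questionnaires. The only app use that Section 5.7.2 and Table 1 schedule is making those entries. Using the app in the patient's place therefore has little or no permitted content.

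**Step 3: does changing the connective suffice?** No. Under *and*, the third row becomes eligible: a patient who cannot use the app, admitted because a carer will use it. The carer may not make the entries, so the contradiction from Step 2 remains.

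**Step 4: the route to the outcomes.** Sections 4.2 and 5.5 place the formal eligibility assessment after consent, so the criterion can feed the screen-failure count. It also determines who is in the app arms, whose daily use is the second primary outcome. Section 7.1 plans 5 sites with up to 12 patients each, 5 × 12 = 60. One site that reads the sentence differently from the rest therefore selects up to 12/60 = 20% of the sample under a different rule.

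**The case against.** The strongest reply is that the intended meaning is plain. The carer paragraph makes support optional. Section 9.1, in describing who is left out, speaks of patients without access to technology or a good grasp of it, and does not mention capable patients who lack a carer. The no-exception sentence in Section 5.1 bars waivers and does not settle how an awkward sentence is to be read. Many sites would probably apply the sensible meaning. This lowers the likely harm. It does not make the sentence correct, and it leaves the carer contradiction in place.

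Three stronger readings are tempting, and the documents do not support them.

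- *A large loss of eligible patients.* A reader might assume that 80% of patients are app-capable, that 60% have a carer and that the two are independent. That gives 0.8 × 0.6 = 48% eligible as written against 1 − 0.2 × 0.4 = 92% under *and*. With 70–90% capable and 40–80% with a carer, the ranges are 28–72% and 82–98%. None of these inputs is in the Protocol. Nor can the results be set against the 5% screen failure in Section 7.1: the treating clinician makes a preliminary check (Section 5.4), so many patients ruled out here might never reach formal screening.
- *Both harms at once.* Under the literal reading everyone admitted is app-capable, so nobody enters in reliance on a carer. Under the reading by intent, capable patients without a carer are not turned away. A site that holds to one reading does not suffer both harms; they coexist only across sites that differ.
- *Certain breach, or proxy entries scored as adherence.* A carer might open and navigate the app while the patient speaks or gives the answers, which can pass as help with access. The paper questionnaire arm needs no app. Proxy completion is prohibited twice, so a known instance is a deviation to be documented under Section 9.5. Nothing in the text says that it would count as compliance.

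**Conclusion.** The point holds as a wording fault in a stated eligibility rule. Read as written, criterion 1 excludes app-capable patients who have no carer, against the optional carer support in Sections 5.2 and 5.4. Its carer clause contradicts the carer rule in those same sections.

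The consequence is conditional. If sites differ in their reading, they enrol different patients and the screen-failure count is affected. If carers then make entries, so is the compliance proportion judged against 75%.

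The size cannot be derived. The Protocol gives neither the share of this trial population who can use the app nor the share with a carer. The smartphone and internet figures in Section 1.3 describe the general public and say nothing about carers. The conclusion rests on the wording alone and needs no assumed rates.

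Severity: should-fix. The study is descriptive, with 60 patients and no hypothesis test, and sensible reading at sites would limit the harm. The correction is nevertheless simple, and the criterion bears on both primary outcomes.

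**What to change.** Reconcile the passages by rewording criterion 1 in Section 5.2 and in the Study Summary, for example: *Unable to complete the app videos or questionnaires themselves, even with a carer helping them to access the tool; or without a suitable device, whether their own or one provided by a carer.* Here *or* is the right connective, because each half alone prevents participation. Delete the clause that has the carer using the app for the participant. The carer paragraphs in Sections 5.2 and 5.4 can then stand unchanged.

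Merely replacing *or* with *and* would not be enough: it would admit a patient who cannot make entries and whose carer may not make them.

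The cost is a one-sentence amendment in two places. The downside is that patients who could take part only through proxy completion stay out, as the carer rule already requires. Recording carer support in the eCRF, and reporting adherence with and without the supported patients, would be useful but is optional.
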